
Data analysis
	
The primary aim of the study is to assess the effect of bimagrumab on body fat mass at Week 48 of the treatment period compared to baseline.
 
The study design enables evaluation of efficacy based on the following dual criteria: 1) statistical significance (superior treatment effect, 1-sided 10% level) in fat mass; and 2) clinical relevance of the change in fat mass (median treatment effect of at least 5%). Weight loss of 5% has been shown to translate into clinical benefit in an overweight and obese population with T2D. Fat mass loss of a similar magnitude to 5% weight loss is expected to translate into similar clinical benefits, (such as on glycemic control) in a similar population.
 
The randomization will be stratified by BMI category (≥ 28.0 kg/m² and ≤ 33.0 kg/m², or > 33.1 kg/m² to ≤ 40.0 kg/m²) in order to achieve an approximate balance of BMI distribution across the two treatment groups. The cutoff value of 33 kg/m² represents the expected median BMI in the population based on internal data; therefore, the two randomization strata are expected to be of similar size. However, equal size strata will not be enforced. A minimum of 10 subjects will be targeted for enrollment in the smaller stratum to ensure acceptable precision of the treatment effect in both strata (see Section 11.7).
 
A longitudinal model describing fat mass over time will be used, using all of the data collected from both randomization strata and adjusting for baseline fat mass, treatment arm, baseline BMI. Variables indicating time and time by treatment interaction will be included. An unstructured within-subject covariance will be used. The change in fat mass at Week 24 will be estimated from that model. In addition, the proportion of subjects reaching at least 5% fat loss at Week 24 will be presented by treatment

	group.
Key words	Bimagrumab, type 2 diabetes, obesity, myostatin, MRI, DXA

1 Introduction

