3.1 Study design

This is a non-confirmatory, randomized, subject and investigator blinded, placebo-controlled, parallel arm study, investigating a 48-week treatment period with i.v. bimagrumab 10 mg/kg in overweight and obese subjects with type 2 diabetes. Approximately 68 subjects are planned to be enrolled and randomized

Company Confidential Information

Screening (Days -21 to -8)

Potential subjects will undergo an onsite screening visit to determine their eligibility for the study (see enrollment criteria [Section 4](#)). Subjects who qualify for enrollment following screening will be scheduled for baseline assessments.

The investigator must recommend a lifestyle intervention ([U.S. Department of Health and Human Services Food and Drug Administration Center for Drug Evaluation and Research 2008](#)) that includes dietary counseling for weight loss with a daily caloric deficit of approximately 500 kcal, with a diet that follows the American Diabetes Association (ADA) guidance for optimal glycemic control, and with protein intake of at least 1.2 g/kg/day to support muscle anabolism.

Subjects must be encouraged to follow a diet containing approximately 45-50% of calories as carbohydrate, 20-25% protein, and 30% fat. Subjects will receive counseling for physical activity and will be encouraged to follow the ADA walking program guidelines (please refer to the SOM). These interventions will be initiated at screening after eligibility is confirmed.

Baseline (Days -7 to -1)

Prior to dosing (Day 1), subjects who are eligible for enrollment following screening will return to the clinic to undergo baseline assessments as defined in [Section 8.1](#)

(Assessment schedule). To facilitate study conduct, subjects may opt to be domiciled on Day -1 to complete baseline assessments prior to dosing on Day 1. Subjects will receive a mobility tracker device to monitor their physical activity.

Randomization and Dosing (Day 1)

Eligible subjects, based on screening and baseline assessments, will be randomized in a 1:1 ratio to receive either bimagrumab or placebo. Randomization will be stratified according to baseline BMI into 2 strata:

- BMI between 28.0 kg/m² and 33.0kg/m² (inclusive) and
- BMI above 33.1 kg/m² and up to 40.0 kg/m² (inclusive).

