3.2 Rationale for study design

The rationale for key elements of the study design include:

- **Randomization:** To decrease the chance of an imbalance in subject characteristics (e.g., age, BMI) between treatment groups.
- **Stratification:** BMI was selected as a stratification parameter as it is an important predictor of response for parameters of body composition/body weight and HbA1c (internal data). The expected median value for BMI in this subject population is 33 kg/m² (internal data), therefore 2 strata above and below/inclusive of the median will ensure a balanced representation of subjects between placebo and active drug in each strata, i.e. strata of approximately similar size between the 2 arms.
- **Subject- and investigator-blinding:** To mitigate the risk of bias in treatment allocation, reporting and causality assessment of adverse events. Furthermore, this design decreases the potential confounding effect of intentional or unintentional behavioral changes made by subjects who are aware of their treatment assignment

- **Placebo arm:** Inclusion of a placebo group will allow the analysis of whether or not bimagrumab treatment is more effective than a standard treatment approach based on lifestyle intervention.
- **Lifestyle interventions:** Trials with anti-obesity agents have to demonstrate treatment benefits on body weight/composition on a background of first line-therapy with lifestyle interventions. The daily caloric deficit of 500 Kcal with approximately 45-50% calories from carbohydrate, 20-25% from protein and 30% from fat is a standard approach and is expected to induce weight loss over the treatment period. It may also enhance the effect of bimagrumab on body composition and body weight. The American Diabetes Association (ADA) walking program is tailored to the type of population in this study and is a gentle, easy to implement approach for physical activity.

Company Confidential Information

Electronic methods to support participants in making behavioral changes to promote weight loss may also be utilized.

- **Adequate protein intake:** Protein content of 1.2 g/kg/day is recommended to ensure adequate dietary intake during the period of muscle growth.

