6.5 Treatment assignment and randomization

Treatment is assigned by stratified randomization for two strata based on the patient's baseline BMI. The strata have the following randomization numbers:

- BMI between 28.0 kg/m² and 33.0 kg/m² (inclusive): 5101 – 5150
- BMI between 33.1 kg/m² and up to 40.0 kg/m² (inclusive): 5201 – 5250

The randomization number is used to identify which strata the patient belonged to at randomization and which treatment the patients have been randomized to receive.

The Patient number assigned to a patient at screening remains the unique identifier for the patient throughout the study. For information on patient numbering, please see 'Subject numbering' section in the SOM.

The randomization numbers will be generated using the following procedure to ensure that treatment assignment is unbiased and concealed from subjects and investigator staff. A randomization list will be produced by, or under the responsibility of, Novartis Drug Supply Management using a validated system that automates the random assignment of treatment arms to randomization numbers in the specified ratio.

BMI was selected as a stratification parameter as it is an important predictor of response on parameters of body composition/body weight and HbA1c (internal data). The expected median value for BMI in this patient population is 33 kg/m² (internal data); therefore, 2 strata above and below/inclusive of the median will ensure a balanced representation of patients between placebo and active drug in each strata, i.e. strata of approximately similar size between the 2 arms. Equal size strata will not be enforced, but a minimal size of 10 will be required for the smaller stratum in order to ensure adequate precision of treatment effect estimation in both strata.

The randomization scheme for patients will be reviewed and approved by a member of the Randomization Office.

Follow the details outlined in the Site Operations Manual regarding the process and timing of treatment assignment and randomization of subjects.

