11.4.2 Statistical model, hypothesis, and method of analysis

The study design enables evaluation of efficacy based on the following dual criteria 1) statistical significance (superior treatment effect, 1-sided 10% level) in fat mass; and 2) clinical relevance of the change in fat mass (estimated median treatment effect of 5% or more). Weight loss of 5% has been shown to translate into clinical benefit in an overweight/obese population with T2D (Franz et al 2015). Fat mass loss of a similar magnitude to the weight loss is expected to translate into similar clinical benefits (such as on glycemic control) in a similar population.

The randomization will be stratified by BMI category (≥ 28.0 kg/m² and ≤ 33.0 kg/m², >33.1 kg/m² to ≤ 40.0 kg/m²) in order to achieve an approximate balance of BMI distribution across the two treatment groups. The cutoff value of 33 kg/m² represents the expected median BMI in that population (based on internal data); therefore the two randomization strata are expected to be of similar size. However, equal size strata will not be enforced. A minimum of 10 patients will be targeted for enrollment in the smaller stratum to ensure accurate precision on the treatment effect in both strata (see Section 11.7).

The primary endpoint will be analyzed using a mixed effects model. This model will have change from baseline in kg fat mass as the dependent variable, treatment arm, time, time*treatment interaction as fixed effects, and a subject level random intercept. Baseline fat mass and baseline BMI value may be included in the model as covariates. Data collected from both randomization strata (BMI category at randomization) will be included in the model. The change from baseline (absolute) in kg fat mass at Week 48 will be estimated from that model and will be summarized graphically and in tabular form. No transformation (logarithmic or otherwise) of body weight will be done for analysis. An unstructured within-subject covariance will be used.

The evaluation of efficacy is based on the following dual criteria:

1. statistical significance (superior treatment effect, 1-sided 10% level) in fat mass; and
2. clinical relevance of the change in fat mass (estimated median treatment effect of 5% or more) at Week 48.

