### 1.4 Study design and treatment

This is a non-confirmatory, randomized, subject and investigator blinded, placebo-controlled, parallel arms study, investigating a 48-week treatment period with intravenous bimagrumab 10mg/kg in overweight/obese patients with type 2 diabetes. Approximately 68 patients (34 receiving active treatment and 34 placebo) are planned to be enrolled and randomized. The randomization will be stratified according to baseline BMI in two strata:

- BMI between 28 kg/m^2 and 33 kg/m^2 (inclusive) and
- BMI above 33 kg/m^2 and up to 40 kg/m^2 (inclusive),

in order to achieve an approximate balance of BMI distribution across the two treatment groups.

Figure 1-1: Study Design

Based on the latest version of protocol amendment, an additional visit at week 2 has been added coded as Visit 115.

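### Do the differing definitions of the upper BMI stratum, and the 10-patient minimum for the smaller stratum, need correcting?

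*Protocol*

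**What the plan says.** The lower stratum is BMI 28.0 to 33.0 inclusive in every place. The upper stratum is written in three ways:

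- Above 33.1: Section 3.1 has "BMI above 33.1 kg/m² and up to 40.0 kg/m² (inclusive"; the protocol synopsis (Data analysis) has "≤ 33.0 kg/m², or > 33.1 kg/m² to ≤ 40.0 kg/m²"; Section 11.4.2 has "≤ 33.0 kg/m², >33.1 kg/m² to ≤ 40.0 kg/m²".
- From 33.1: Section 6.5, with the list numbers, has "BMI between 33.1 kg/m² and up to 40.0 kg/m² (inclusive): 5201 – 5250".
- Above 33: SAP 1.4 has "BMI above 33 kg/m 2 and up to 40 kg/m 2 (inclusive".

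The intent is stated separately. Section 11.4.2 says "The cutoff value of 33 kg/m² represents the expected median BMI in that population (based on internal data", and Section 3.2 explains that "2 strata above and below/inclusive of the median will ensure a balanced representation of subjects" between the arms.

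On stratum size, Section 6.5 says "a minimal size of 10 will be required for the smaller stratum in order to ensure adequate precision of treatment effect estimation". The synopsis and Section 11.4.2 make 10 a target and refer to Section 11.7 for support. Section 11.7 gives only the overall calculation: 68 recruited, at most 30% dropout, at least 48 completers, a 6% effect, an SD of 6.5% and about 70% power.

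**The concern.** Read literally, the synopsis and Sections 3.1 and 11.4.2 give no stratum to a BMI above 33.0 and up to 33.1. Rounding to one decimal does not remove this, because a recorded 33.1 is still not above 33.1. If sites and programmers worked from different sections, the stratum in the data could differ from the one used at randomization.

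The minimum of 10 comes with an assurance about precision in both strata, and the section cited for it contains no such calculation. If stratum estimates were to guide decisions, a reader could trust an estimate from 10 patients far more than the protocol's own SD allows. The minimum is also mandatory in one place and a target in two others, and it fits oddly with lists of 50 numbers each.

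**Working it through.** **The plan's own figure.** Inputs from Section 11.7: 24 completers per arm, effect 6, SD 6.5, one-sided 10% test, and an estimate of at least 5. SE = 6.5 × √(2/24) = 1.876. The significance bound is 1.2816 × 1.876 = 2.40, so the 5-point threshold decides. Power = 1 − Φ((5 − 6)/1.876) = 70.3%, against the stated 70% or so. No stratum boundary or stratum size enters this calculation.

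**Boundary, by recorded BMI at one decimal.**

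| Recorded BMI | Synopsis, 3.1, 11.4.2 | 6.5 | SAP 1.4 |
|---|---|---|---|
| 33.0 | lower | lower | lower |
| 33.1 | none | upper | upper |
| 33.2 | upper | upper | upper |

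One recorded value is affected, and no place puts it in the lower stratum. Section 6.5 assigns the numbers (5101–5150 and 5201–5250) and resolves it in the same way as the SAP.

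**How many patients.** The documents give a median of 33 and a range of 28 to 40. The shape is assumed. A flat density above the median gives 0.5 × 0.1/7 = 0.71% in the 0.1-unit band. A normal truncated to the range, with SD 2 to 5, gives 2.01% to 1.06%. For 68 patients that is about 0.5 to 1.4. The chance of at least one, 1 − (1 − p)^68, is 39% to 75%. This applies only if the above-33.1 wording is used; under Section 6.5 at one decimal it is zero.

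**Smallest stratum.** Each list has 50 numbers, so N patients put at least N − 50 in the smaller stratum: 68 − 50 = 18, and 60 − 50 = 10. The minimum of 10 therefore adds something only if fewer than 60 are randomized.

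**Precision.** SE = 6.5 × √(1/a + 1/b), half-width = t × SE with a + b − 2 df. Even splits are assumed, as near as the total allows.

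| Stratum | Split | SE | 80% half-width | 95% half-width |
|---|---|---|---|---|
| 10, no dropout | 5 v 5 | 4.11 | 5.7 | 9.5 |
| 7 completers (10 × 0.7) | 4 v 3 | 4.96 | 7.3 | 12.8 |
| 18, no dropout | 9 v 9 | 3.06 | 4.1 | 6.5 |
| 12 completers (18 × 0.7 = 12.6) | 6 v 6 | 3.75 | 5.1 | 8.4 |
| 13 completers | 7 v 6 | 3.62 | 4.9 | 8.0 |
| 34, the size expected if 33 is the median | 17 v 17 | 2.23 | 2.9 | 4.5 |

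If the error is pooled over the whole trial (48 − 4 = 44 df, t = 1.301), the 80% half-widths for 12 and 13 completers are 1.301 × 3.75 = 4.9 and 1.301 × 3.62 = 4.7.

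**The case for a change.** The best case for a change is that all of this is current, unredacted text that contradicts itself. The randomization number is the record of stratum, so the definition ought to be unique. No rounding rule is given. Weight is scheduled at screening, baseline and Day 1, and Section 6.5 does not say which one gives the baseline BMI. The precision assurance has no support where the reader is sent, and at 10 patients the 95% half-width (9.5) exceeds the assumed effect of 6 even before dropout. Rewording would cost almost nothing.

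The textual part stands: three wordings of one boundary, a minimum that is required in one place and targeted in two, and a cross-reference that leads nowhere. The consequences do not follow.

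- A patient near the boundary is randomized 1:1 whichever list is used, so the comparison of arms is not biased. At most, the BMI balance shifts by a patient or so.
- Analysts can read the stratum from the randomization number and need not recompute it from height and weight. That also covers a value such as 33.04, which rounds to 33.0 but lies above 33 unrounded.
- The schedule has a visit named Baseline with a weight, and that is the natural reading of baseline BMI.
- The wide intervals belong to a stratum of 10, which the lists rule out at 68 patients. At 18, the 80% half-width before dropout is inside the 5-point threshold, and after dropout it is about at it. That threshold applies to the pooled point estimate; it is not a standard for interval width, and the plan sets none for strata.
- A minimum of 10 beside lists of 50 is redundant at 68, not contradictory. Enrolment is only approximately 68, so the minimum could still matter if recruitment fell below 60. Lengthening the lists to 58 would lower the guaranteed size from 18 to 10 and make stratum precision worse.

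**Conclusion.** These are clerical slips, and no change to the plan follows. The intended split at 33 is clear from the stated cutoff, the rationale in Section 3.2, the lower stratum's fixed upper end and the SAP. The section that runs the randomization implements it. The literal gap concerns one recorded value, about 0.5 to 1.4 patients of 68 under the assumed distributions, and none if Section 6.5 is followed. The visible primary model (Section 11.4.2 and SAP 6.1.3) has no stratum term and may adjust for the BMI value itself, so neither the primary estimate nor the power of about 70% depends on the wording.

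The precision remark is unquantified and its cross-reference is empty, but no visible decision uses a stratum estimate, and any such estimate can be reported with its own interval.

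This rests on BMI being recorded to one decimal (the protocol writes its stratum limits that way but states no rule), on about 68 being randomized, and on no stratum-level decision rule in the redacted parts of the analysis sections. If the documents are amended for another reason, the wording can be aligned then; no result would change.

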6.6 Treatment blinding

This is a subject- and investigator-blinded study. Subjects and investigators will remain blinded to study treatment throughout the study, except where indicated below.

Site staff

With the exception of any unblinded site staff identified below, all site staff (including study investigator and study nurse) will be blinded to study treatment throughout the study.

- Unblinded pharmacist

Unblinding a single patient at site for safety reasons (necessary for patient management) will occur via an emergency system in place at the site (see [Section 6.8](#) Emergency breaking of assigned treatment code).

IMPORTANT: Drug product will be supplied in bulk. Due to the difference in preparation methods between the active and placebo treatments, an unblinded pharmacist or other qualified trained personnel, who is independent of the study team, will be required. This unblinded pharmacist will receive treatment allocation cards from Drug Supply Management with the appropriate treatment allocation numbers. Appropriate measures must be taken by the unblinded pharmacist to ensure that the treatment assignments are concealed from the rest of the site staff. Any potential visible difference in treatments will be concealed by the use of an opaque sleeve.

Sponsor staff

The following unblinded sponsor roles are required for this study:

- Unblinded field monitor(s)
- Unblinded clinical staff managing drug re-supply to site
- Unblinded sample analyst(s) (PK blood)

The unblinded field monitors are required to review drug accountability and allocation at site. The unblinded monitors are not provided with a randomization list directly but will be unblinded through review of source documentation compiled by the unblinded pharmacist, which details treatment allocation to individual subjects. The unblinded monitors will also be able to review the treatment allocation cards/randomization list provided to the unblinded pharmacist.

Sponsor clinical staff are required to assist in the management and re-supply of investigational drug product. These individuals are not provided with randomization lists directly, but may be unblinded through communication of drug re-supply needs via the unblinded site pharmacists.

The sample analysts will receive a copy of the randomization schedule (via request to the Randomization Office), to facilitate analysis of the samples. The sample analysts will provide the sample data to the study team under blinded conditions unless otherwise allowed.

The study statistician will be able to access the randomization list for interim analyses and is allowed to share unblinded information with the rest of the clinical team as appropriate for internal decision purposes, as outlined in [Table 6-2](#). For example, unblinded summaries and unblinded individual data can be shared with the team for interim analyses.

Study programmers and other personnel involved in study data analysis (e.g. biomarker expert) are allowed to access treatment assignment information for the purpose of conducting interim analyses.

The clinical trial team is allowed to share unblinded results with other sponsor staff (e.g. decision boards) as required for internal decision making on the study or the project at the time of interim analyses while the study is ongoing.

All unblinded personnel will otherwise keep randomization lists and data or information that could unblind other study team members confidential and secure except as described above.

Following final database lock all roles may be considered unblinded.

Table 6-2 Blinding levels

Role	Time or Event			
	Randomization list generated	Treatment allocation & dosing	Safety event (single subject unblinded)	Interim Analysis
Subjects	B	B	UI	B
Site staff	B	B	UI	B
Unblinded site staff (see text for details)	B	UI	UI	UI
Drug Supply and Randomization Office	UI	UI	UI	UI
Unblinded sponsor staff (see text for details)	B	UI	UI	UI
Statistician/statistical programmer/data analysts	B	B	UI	UI
Independent committees used for assessing interim results	B	UI	UI	UI
All other sponsor staff not identified above	B	B	UI	UI

B Remains blinded

NA Not applicable

UI Allowed to be unblinded on individual patient level

6.7 Treating the subject

Bimagrumab or placebo will be administered to the subject via the following route of administration: i.v. by infusion pump.

Administrations will be performed at the study site. See the Site Operations Manual for further details.

Sponsor qualified medical personnel will be readily available to advise on trial related medical questions or problems.

6.8 Emergency breaking of assigned treatment code

Emergency unblinding must only be undertaken when it is essential to treat the subject safely and efficaciously. Most often, study treatment discontinuation and knowledge of the possible treatment assignments are sufficient to treat a study subject who presents with an emergency condition. A complete set of emergency code break cards will be provided to the investigator site(s) and a complete set will be available at Novartis. All code break cards must be retained until the end of the study and returned to Novartis. They must be stored in a secure place but be accessible to the investigator 24 hours per day in case of emergency. The investigator will receive a blinded code break card for each subject, with the details of study treatment covered by a removable, scratch-off cover. In an emergency, the scratch-off cover can be removed to determine the treatment. The scratch-off covers are not to be removed for any reason other than an emergency. When the investigator removes the scratch-off cover he/she must note the date, time, and reason for removing it and retain this information with the case report form documentation. **The unblinded treatment code must not be recorded on the CRF.** The investigator must also immediately inform the study monitor that the code has been broken.

It is the investigator's responsibility to ensure that there is a dependable procedure in place to allow access to the code break cards at any time in case of emergency. The investigator will need to provide:

- protocol number
- study drug name (if available)
- subject number.

In addition, the investigator must provide oral and written information to inform the subject how to contact his/her backup in cases of emergency when he/she is unavailable to ensure that un-blinding can be performed at any time.

An assessment will be done by the appropriate site personnel and sponsor after an emergency un-blinding to assess whether or not study treatment should be discontinued for a given subject and, if applicable, whether the subject can continue into the next trial phase (e.g., an unblinded extension).

